COMIRB Protocol

COLORADO MULTIPLE INSTITUTIONAL REVIEW BOARD
[name] [contact] [contact]

Protocol Version 3, 07/09/2015

Project Title: Aspiration in Acute Respiratory Failure Survivors

Principle Investigator: [name] MD

I. Hypothesis and Specific Aims

We hypothesize that the BSE assessment of swallowing certain consistencies will provide the most accurate diagnosis of aspiration.

A. Specific Aim #1: To develop a BSE-based non-invasive clinical prediction rule (CPR) that will accurately and efficiently diagnose aspiration in ARF survivors.

B. Specific Aim #2: To identify abnormalities in laryngeal structure and swallowing physiology that are associated with aspiration in ARF survivors.

Study Design: Prospective cohort study of patients with acute respiratory failure who require mechanical ventilation for more than 48 hours.

Inclusion Criteria:

1. Admission to an ICU.
2. Mechanical ventilation with an endotracheal tube for greater than 48 hours.

Exclusion Criteria:

1. Age < 18 years
2. Contraindication to enteral nutrition administration.
3. Pre-existing or acute primary central or peripheral neuromuscular disorder
4. Pre-existing history of dysphagia or aspiration.
5. Pre-existing head and neck cancer or surgery.
6. Presence of a tracheostomy.
7. Coagulopathy resulting in uncontrolled nasal or pharyngeal bleeding.
8. Unable to participate due to altered mental status
9. Extubated for greater than 72 hours.
10. Inability to obtain informed consent from patient or an appropriate surrogate.
11. Pregnancy
12. Imprisoned at the time of admission, anytime during the hospitalization, or anytime during the follow up period

First, a SLP will perform a comprehensive BSE on each ARF survivor.

Subsequently a second blinded SLP/investigator will perform the FEES to determine whether aspiration is truly present. The FEES examination will also identify abnormalities associated with aspiration.

For Aim #1: Primary Outcome Variable: Aspiration (PAS score of ≥ 6) on the FEES with any of the five feedings. A PAS score of ≥ 6 includes patients with both silent and non-silent aspiration.

Statistical analysis: Recursive partitioning or Classification and Regress Tree (CART) analysis creates a tree that asks a series of yes/no questions, taking the user down different branches depending on the answers. At the end of each branch will be an estimated probability of outcome.

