Because the mechanisms responsible for aspiration are essentially unknown, there are no medical therapies to treat or prevent aspiration in ARF survivors.²⁶ Currently SLPs treat patients with suspected aspiration by restricting oral nutrition, adjusting the consistency of their food or liquids, or teaching patients different swallowing maneuvers.⁷⁷⁻⁹⁰ All of these interventions limit the chance of aspiration but do not treat the underlying cause of the swallowing dysfunction.⁷⁷⁻⁹⁰ There are several abnormalities in ARF survivors that may be responsible for dysphagia and subsequent aspiration (Figure 2). These abnormalities may be caused by the prior endotracheal tube, deconditioning, critical illness polyneuromyopathy, reduced pharyngeal clearance, and/or limited respiratory reserve.^{27-31;52;91-96} We identified specific abnormalities in laryngeal function and swallowing physiology that are associated with aspiration in ARF survivors (see preliminary data).⁵² Additional studies are needed to delineate the

FIGURE 2

[figure not shown]

mechanisms responsible for aspiration in these patients.

PRELIMINARY DATA: 1. Longer duration of mechanical ventilation is associated with dysphagia.⁵ We conducted a cohort study of 446 ARF patients admitted to the Medical ICU who required mechanical ventilation and received a BSE. Patients with prior neuromuscular disorders were excluded. Dysphagia was present in 84% of patients (mild in 52% and moderate/severe in 48%). After adjustment, longer duration of mechanical ventilation was independently associated with moderate/severe dysphagia (AOR 2.84 [1.78-4.56], p <0.01). *These results suggest that dysphagia is common in ARF survivors.*

[figure not shown]
2. In ARF survivors, dysphagia can persist until hospital discharge and is associated with prolonged hospitalization and delayed oral nutrition.⁵ Moderate/severe dysphagia was independently associated with the composite outcome of pneumonia, re-intubation, or in-hospital death (AOR 3.31 [1.78-4.56], p<0.01) (Figure 3). In ARF survivors, dysphagia was still present in 55% of patients at hospital discharge. Hospital duration was longer in ARF survivors with dysphagia compared to those without dysphagia (8 [5-15] days vs 5 [3-8] days after the initial BSE was performed, p<0.01). Patients with moderate/severe dysphagia were more likely to be kept NPO after the initial BSE (74% vs 15%, p<0.01) and receive a surgical feeding tube during hospitalization (15% vs 5%, p<0.01).

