Next, a SLP will perform a comprehensive BSE on each ARF survivor, and a second blinded SLP will perform the FEES to determine whether aspiration is truly present. The order of the BSE and FEES exams will be randomized. The reason for the random order of the tests is that after several swallows, a patient who has not eaten orally in several days or weeks will start to do better as the system "wakes up". If the BSE always precedes the FEES, it might lead to a false result – it would show more aspiration on the BSE than the FEES. But it won't be because the BSE was showing a false positive; in fact it is just that the patient started to improve by the time he got the second exam.

2. Bedside Evaluation:

The BSE protocol should be performed within 24 hours from the time that the informed consent was signed. The BSE protocol will be performed in the same order and the amount of each bolus delivered in the exact manner for all patients. Unless there are medical restrictions (due to femoral lines, sacral wounds, etc), all BSEs should be performed in a sitting position. The SLP will document the patient position that the BSE was

performed.

Part 1: Initial Assessment: The SLP will review the subject's medical record and become knowledgeable with the patient's medical history. The patient should be seated with the head of the bed as elevated as possible. A physical exam of the aerodigestive system will be performed including respiratory rate; saliva formation; lip seal; tongue movement, strength, and coordination; palate movement, gag reflex; cough reflex; and voice quality/dysphonia. In addition, the SLP will also determine cough strength in L/min using a peak flow meter (HealthScan, Cedar Grove, NJ).

Part 2: Standardized consistency testing: The SLP will then administer five standard consistencies.¹⁰⁶ Some consistencies will be tested twice with different amounts. In general, the bolus should be administered with a medicine cup. A straw should only be used for the 3 ounce water test and the 2 ounce patient controlled trials.

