Part 3: Three Ounce Water Swallow Test (3-WST): During the standardized 3-WST, patients receive three ounces of water and are instructed to drink the entire amount, via cup or straw, completely and without interruption (the cup can be held to the patient's mouth by the SLP).^{74;76;109} The 3-WST will be scored as pass/fail. Criteria for failure of the 3-WST are: the inability to drink the entire amount, coughing or choking up to 1 minute after completion, or the presence of a wet-hoarse vocal quality.

At this point the SLP will document their diet recommendations, and whether further invasive testing (MBSS or FEES) is indicated.

Subsequently, the SLP can perform additional testing including specific maneuvers. The results of these additional tests will be recorded in the CRF. The SLP will then document their diet recommendations that include the knowledge gained from the additional testing. Again the SLP will document whether further invasive testing (MBSS or FEES) is indicated.

Based on these recommendations, the patient will be allowed to advance their diet prior to the performance of the FEES, if indicated.

The coordinator should make sure that the BSE CRF is completely filled out before the SLP who completed the test leaves the ICU.

The BSE form for consistency testing is attached as Appendix.

3. FEES examination: The SLP will review the subject's medical record and become knowledgeable with the patient's medical history. The FEES examination will be performed by a second SLP who is blinded to the results of the BSE. The FEES should be performed within approximately 4 hours of the BSE.

Similar to the BSE, the patient should be seated with the head of the bed as elevated as possible. At the discretion of the SLP/investigator, Afrin and Lidocaine spray can be administered into the nasal passage before the laryngoscope is inserted. The use of these medications will be noted in the case report form.

Part 1: First the SLP will perform and videotape the examination of the upper airway. Velar closure, base of the tongue retraction, laryngeal elevation, right and left vocal cord/arytenoid mobility, right and left pharyngeal wall medialization, epiglottic retroflexion, granuloma formation, and upper airway edema will be assessed.

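### In patients examined at the bedside first, what happens before the FEES can depend on the BSE result, and the plan does not account for this

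*Combined protocol and SAP*

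**What the plan says.** **Between the exams.** Study Procedures, 2. Bedside Evaluation, Part 3 has the speech-language pathologist (SLP) record a diet recommendation straight after the 3-ounce water test. Then: "Subsequently, the SLP can perform additional testing including specific maneuvers". A second recommendation follows, and then: "Based on these recommendations, the patient will be allowed to advance their diet prior to the performance of the FEES, if indicated". Results of the additional tests are to go in the CRF. On timing, section 3 (FEES examination) says: "The FEES should be performed within approximately 4 hours of the BSE".

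**Order.** The end of 1. Baseline assessments says "The order of the BSE and FEES exams will be randomized". The reason given is that "after several swallows, a patient who has not eaten orally in several days or weeks will start to do better", so a fixed order could give a misleading comparison. The synopsis (section I) and the Significance section describe a fixed sequence: "First, a SLP will perform a comprehensive BSE on each ARF survivor", with the FEES afterwards.

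**Blinding.** Section 3 says the second SLP is blinded to the BSE results. The same paragraph begins: "The SLP will review the subject's medical record and become knowledgeable with the patient's medical history".

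**Maneuvers.** The Background names diet restriction, changed consistency and taught maneuvers as current SLP practice for suspected aspiration, and comments: "All of these interventions limit the chance of aspiration but do not treat the underlying cause of the swallowing dysfunction".

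**Analysis.** The Aim 1 analysis, including Additional Considerations, has no term for test order, no stratification by order and no handling of intake or maneuvers between exams. The appendix forms carry date and time, so the order performed can be derived. They have no field for additional testing or for oral intake before the FEES.

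**The concern.** A diagnostic accuracy estimate assumes that the reference standard measures the same state as the index test and that the index result does not influence it. Here, in BSE-first patients, the bedside recommendation helps decide whether the patient eats before the FEES, and the plan itself says that swallowing changes performance. If some bedside-negative aspirators no longer aspirate at FEES after eating, false negatives are recorded as true negatives and NPV looks better than it is. If some bedside-positive aspirators no longer aspirate after trying a maneuver, true positives are recorded as false positives and PPV looks worse.

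FEES aspiration is the primary outcome for Aim 1, so the tree and the accuracy estimates for each consistency all depend on it. A second route is observer knowledge: an examiner who sees a diet order issued after the BSE can guess its result.

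**Working it through.** The plan gives no figure to reproduce on this point. The check is a comparison of the sections and then an illustrative reclassification.

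**Which patients are exposed.** Under the randomised order, only BSE-first patients can have BSE-dependent exposure before the FEES. Under the synopsis, all 225 can. Randomisation balances a general warm-up effect between the order groups. It cannot balance exposure that follows from the BSE result within the BSE-first group.

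**What is affected.** BSE Parts 1 to 3 and the first recommendation are recorded before any maneuver or diet change. The index data are therefore intact, and only the FEES result is at risk.

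**Inputs.** Prevalence 50% (pilot of 26 patients) or 44% (Significance section). Sensitivity 38% and specificity 75% (Table 1, thin liquids). Assumed, because the documents are silent: 1:1 order, and the shares a+ and a− of bedside-positive and bedside-negative aspirators who become FEES-negative in BSE-first patients.

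**Formulas.** Let s be the share of patients examined BSE-first. TP′ = TP(1 − s·a+), FP′ = FP + s·a+·TP, FN′ = FN(1 − s·a−), TN′ = TN + s·a−·FN.

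**Start, prevalence 50%.** TP = 0.50 × 0.38 = 0.190, FN = 0.310, FP = 0.125, TN = 0.375. PPV = 0.190/0.315 = 60.3%. NPV = 0.375/0.685 = 54.7%.

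**Both shares 20%, s = 0.5.** TP′ = 0.171, FP′ = 0.144, FN′ = 0.279, TN′ = 0.406. Sensitivity = 0.171/0.450 = 38.0%, specificity = 0.406/0.550 = 73.8%, PPV = 0.171/0.315 = 54.3%, NPV = 0.406/0.685 = 59.3%.

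| Prevalence 50% | Sens | Spec | PPV | NPV |
|---|---|---|---|---|
| No conversion | 38.0 | 75.0 | 60.3 | 54.7 |
| Half BSE-first, a− = 20% only | 40.5 | 76.5 | 60.3 | 59.3 |
| Half BSE-first, a+ = 20% only | 35.6 | 72.3 | 54.3 | 54.7 |
| Half BSE-first, both 20% | 38.0 | 73.8 | 54.3 | 59.3 |
| Half BSE-first, both 10% | 38.0 | 74.4 | 57.3 | 57.0 |
| All BSE-first, both 20% | 38.0 | 72.8 | 48.3 | 63.8 |

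At 44% prevalence with half BSE-first and both shares 20%, PPV goes from 54.4% to 49.0%, NPV from 60.6% to 64.6% and specificity from 75.0% to 74.1%, with sensitivity unchanged.

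Sensitivity moves only when the two shares differ, and the two routes push it in opposite directions. With equal shares the table looks the same as after a uniform carry-over of that size. PPV and NPV shift either way.

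**Why exposed patients should not simply be dropped.** Suppose half of the bedside-negative BSE-first patients eat and are excluded, with no conversion at all. A quarter of all bedside-negatives is lost: FN = 0.310 × 0.75 = 0.2325, TN = 0.375 × 0.75 = 0.28125. Sensitivity becomes 0.190/0.4225 = 45.0% and specificity 0.28125/0.40625 = 69.2%. The exclusion selects on the BSE result and distorts sensitivity and specificity more than any row of the table does.

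**Precision of a FEES-first analysis.** Half the cohort at 50% prevalence has about 56 aspirators and 56 non-aspirators. The 95% half-width for sensitivity is 1.96 × √(0.38 × 0.62/56.25) = 12.7 points, against 9.0 in the whole cohort. For specificity it is 11.3 against 8.0.

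**The case against.** The other side has real points.

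- The maneuver sentence gives no trigger and calls the activity testing. A reader might infer that maneuvers go to patients with suspected aspiration and then carry into the FEES. The only support is the Background's account of general practice, which is not a study rule. Nothing shows that patients would use a maneuver uncued during standardised FEES boluses. Diet advance is the better-supported route, because it is explicitly tied to the recommendation.
- A completed BSE already delivers 11 boluses and 3 ounces of water. If improvement follows several swallows, most of it may have happened before any meal, and that general effect is what the randomised order addresses. Nothing in the documents shows that eating within about 4 hours adds more. This limits the likely size but does not remove the result-dependent part.
- Additional test results must already be recorded in the CRF. That is correct, but the appendix form has no place for them and none for oral intake.
- Blinding is stated explicitly. It is, but the plan does not say how the record review is kept from revealing the BSE. That a diet order would be seen is a possibility, not a fact.
- The tree is judged on misclassification, which barely moves: (0.125 + 0.310) = 43.5% to (0.144 + 0.279) = 42.3% with both shares at 20%. This stands, though predictive values are also planned outputs and move more.
- The Significance section weighs aspiration against the harm of delayed feeding, so allowing diet advance may be deliberate. That is a clinical judgement on which this review takes no position.

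**Conclusion.** The concern holds as a possibility that the plan permits and does not handle. In BSE-first patients, BSE-dependent diet advance and optional maneuver testing may change the Aim 1 reference result. Randomised order dilutes this but does not remove it. The sections disagree on whether order is randomised at all, and the FEES examiner's record review could reveal the BSE outcome.

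A reader might go further and conclude that the FEES result is altered, that accuracy is biased, or that NPV is certainly inflated. The documents do not support that. They give no conversion rates, and the maneuver and diet routes can partly offset each other in sensitivity. Neither size nor net direction can be derived.

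With 20% conversion on both routes, 1:1 order, 50% prevalence and the thin-liquid pilot accuracy, whole-cohort PPV would go from 60% to 54%, NPV from 55% to 59% and specificity from 75% to 74%, with sensitivity unchanged. If only one route operates, sensitivity would lie between 35.6% and 40.5% and specificity between 72.3% and 76.5%. If every patient had the BSE first and both routes operated, PPV would be 48% and NPV 64%. All of these rest on assumed conversion rates.

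**What to change.** 1. **Shield the FEES examiner.** Take the history from a coordinator summary or a record view that omits the BSE SLP note and any diet order that follows from the BSE.
2. **Record the exposure.** Add CRF fields for test order, oral intake between the exams and maneuvers tried between the exams.
3. **Analyse by order.** Report Aim 1 accuracy by test order, with a sensitivity analysis in FEES-first patients. Do not exclude patients by intake or maneuver. In FEES-first patients any warm-up falls on the BSE instead, so a difference between the order groups is a warning sign and not a clean estimate of this effect.
4. **Reconcile the text.** Bring the diet-advance and additional-testing sentences in 2. Bedside Evaluation into line with the rationale in 1. Baseline assessments. Bring the synopsis and Significance section into line with the randomised order. No clinical rule on feeding or testing is proposed.

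The cost is some coordinator time, a few CRF fields and one further analysis. That analysis is less precise, because it uses about half the cohort.

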Laryngeal sensation will be assessed by observing the laryngeal adductor reflex (LAR) or a patient response to a light touch/poke to the aerepiglottic folds bilaterally with the tip of the laryngoscope, and scored dichotomously.

Part 2: Standardized consistency testing: The SLP will then administer five standard consistencies in two trials of each consistency with different amounts.¹⁰⁶

Boluses will be administered from lowest to highest aspiration risk: 1) $\frac{1}{2}$ tsp, then 1 tsp ice chips, 2) 1 tsp of nectar thick liquids, then 3 tsp of nectar thick liquids, 3) a 2 ounce patient controlled administration of nectar thick liquids, 4) 1 tsp of pureed solids (applesauce), then 10 mls of pureed solids (applesauce), 5) 5 mls of thin liquids (water or milk), 15 mls of thin liquids (water or milk), and a 2 ounce patient controlled administration of thin liquids and 6) $\frac{1}{4}$ of a graham cracker.¹⁰⁷ The patient will be instructed to chew the graham cracker before swallowing. In order to limit the complexity and duration of our consistency testing, honey-thick liquids will be excluded from the protocol.

Table 3: PAS scoring system

Scale	Enters airway?	Relationship to vocal folds	Ejected from airway?	Effort made to eject?
1	No	--	--	--
2	Yes	Above	Yes	--
3	Yes	Above	No	--
4	Yes	Contacting	Yes	--
5	Yes	Contacting	No	--
6	Yes	Below	Yes	--
7	Yes	Below	No	Yes
8	Yes	Below	No	No

After the swallow, the laryngoscope will be advanced to closely view the patient's airway. The SLP will wait for 10 seconds following the completion of each individual trial before recording the results for that consistency. If necessary, patients will be allowed to drink water between consistency tests to clear any remaining residue from their upper airway.

The entire FEES will be video recorded. The SLP will score each of the trials using the PAS score (Table 3).

In addition for each of the trials of the consistencies, the SLP will record the following two physiological measures:

- 1) Swallowing onset time: The time from first bolus visualization until swallow onset.
- 2) Incomplete bolus clearance: leaving residue in the pharynx or laryngeal vestibule after a swallow.

Using the video recordings, the quantification of the swallowing onset time and incomplete bolus clearance will be determined by a single observer.

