whether the subject had the outcome of interest. Using baseline demographical information, testing for confounding will also be assessed to better understand the relationships between independent variables and outcomes. Based on the enrollment described in Aim #1, we have powered the univariate comparison between our primary independent and dependent variables for these studies. A logistic regression with a sample size between 178 and 271 observations achieves 80% power at a 0.05 significance level to detect an odds ratio between 2.5 and 3.0.

Risks and Justifications of Procedures and Data Collection Tools: Risks of the FEES procedure include patient discomfort, gagging, vomiting, aspiration, mucosal injury, epistaxis, and an adverse reactions to topical anesthetics.^{12, 15-17} One study of 500 consecutive FEES assessments reported the occurrence of minor epistaxis with spontaneous cessation of bleeding in 0.6% of cases.¹⁵ Another survey of SLPs performing a total of 6000 FEES examinations reported 20 cases of epistaxis (0.3%).¹⁸ Vasovagal syncope and laryngospasm, while theoretical concerns, have been shown to occur exceedingly infrequently (a total of two and four cases, respectively, ever reported out of all FEES procedures ever done).¹⁸ None of these reported cases resulted in serious consequences.¹⁸ The 3-WST has been shown to be a safe test in large groups of hospitalized patients.^{11, 19} Our informed consent process will involve a complete discussion of each of these risks, citing reported frequencies of adverse events. Due to the risk of breach of confidentiality, we have assured that all data will be collected and stored in a safe manner. All data at each site, will be stored on a password protected research-specific server, and will not be transferred to any other computer or flash drive. Hard copies of consent forms and other forms will be kept in a locked drawer in a locked office at each enrolling site. Citrix ShareFile, a cloud-based, encrypted HIPAA compliant and University of Colorado IT approved application will be used to share de-identified FEES video recordings between the two enrolling sites. ShareFile will be accessible only to approved research staff and used for the fidelity and scoring of FEES procedures by investigators.

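### The FEES examiner is called blinded to the BSE but must review the medical record without limit and then scores the Aim 1 outcome at the bedside; no procedure protects the blinding

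*Combined protocol and SAP*

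**What the plan says.** All references are to the combined protocol and SAP.

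- **Blinding.** Study Procedures, 3. FEES examination: "The FEES examination will be performed by a second SLP who is blinded to the results of the BSE". The sentence just before it sends that examiner to the medical record: "3. FEES examination: The SLP will review the subject's medical record and become knowledgeable with the patient's medical history". Neither sentence says which entries are off limits.
- **What exists by then if the BSE came first.** At the end of 2. Bedside Evaluation, Part 3: "At this point the SLP will document their diet recommendations, and whether further invasive testing (MBSS or FEES) is indicated". After any additional testing the recommendation is documented again, and "Based on these recommendations, the patient will be allowed to advance their diet prior to the performance of the FEES, if indicated". The BSE form in the Appendix offers nil by mouth among the diet choices for both solids and liquids.
- **Timing.** "The FEES should be performed within approximately 4 hours of the BSE".
- **Who scores the outcome.** The Aim 1 primary outcome is PAS of 6 or more on any feeding. In 3. FEES examination, Part 2, "The SLP will score each of the trials using the PAS score (Table 3"). Results are recorded after a 10-second wait following each trial, and the FEES form, which carries the PAS fields, must be complete before that examiner leaves the ICU.
- **What is read from video.** In the same Part 2, "the quantification of the swallowing onset time and incomplete bolus clearance will be determined by a single observer". These two measures are among the Aim 2 primary outcomes. PAS is not named there.
- **Shared recordings.** Under Risks and Justifications of Procedures and Data Collection Tools, de-identified videos exchanged between the two sites are to be "used for the fidelity and scoring of FEES procedures by investigators". PAS is not mentioned, and no rule says which score counts if there are two.

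**The concern.** Aim 1 asks how well bedside findings predict aspiration on FEES. That question needs a reference reading made without knowledge of the bedside findings. Here the operating instruction (read the record) works against the stated intention (blinded), in the patients whose record may already reflect the bedside verdict.

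The cut between PAS 5 and PAS 6 is whether material contacts the vocal folds or passes below them, which leaves room for judgement. An examiner who has seen that the diet was advanced, or that nothing by mouth was ordered, may resolve a doubtful bolus in that direction. Agreement between BSE and FEES then rises for a reason unrelated to the BSE's merit. Patients who aspirate on FEES but look safe at the bedside are the most exposed. The Background names this kind of missed silent aspiration as a reason to doubt the BSE.

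The planned ten-fold cross-validation offers no protection. Training and test folds carry the same FEES labels, so a label shifted toward the BSE is shifted in both.

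**Working it through.** The plan gives no figure for this point, so there is none to reproduce. The check has two parts.

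**Can the blinding fail while the plan is followed?** For a BSE-first patient:

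1. The first SLP documents diet recommendations.
2. The diet may be advanced on them.
3. Within about 4 hours the second SLP reviews the record.
4. That SLP performs the FEES and scores PAS at the bedside.

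Steps 1, 2 and 4 are stated. Step 3 is stated without a limit. The one link not stated is that step 1 or 2 leaves a trace in the record by step 3. So the failure is possible under the plan as written, but it is not shown to occur.

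**How large could the effect be?** Inputs:

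- Sensitivity 38%, specificity 75%: Table 1, thin liquids. The row (38/75/60/55) is reproduced by 8 aspirators and 8 non-aspirators: 3/8 = 37.5%, 6/8 = 75%, 3/5 = 60%, 6/11 = 54.5%. It is therefore a very small base.
- Prevalence 50%: Preliminary Data, item 5.
- Share with BSE first, *f*: 0.5 if the randomized order is 1:1 (ratio not stated), or 1 if the BSE always precedes the FEES, as the opening design summary and the Significance section read.
- Pull, *r*: the share of BSE/FEES-discordant patients among those with BSE first whose FEES result is scored to agree with the BSE. The documents give no value; 10% and 20% are assumed.

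Per 100 patients: TP = 50 × 0.38 = 19; FN = 31; TN = 50 × 0.75 = 37.5; FP = 12.5; discordant = 43.5.

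With *q* = *f* × *r*: TP′ = TP + *q*·FP, FN′ = (1 − *q*)·FN, TN′ = TN + *q*·FN, FP′ = (1 − *q*)·FP.

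| *f* | *r* | *q* | Sensitivity | Specificity | Results changed in 225 |
|---|---|---|---|---|---|
| any | 0 | 0 | 38.0% | 75.0% | 0 |
| 0.5 | 10% | 0.05 | 19.625/49.075 = 40.0% | 39.05/50.925 = 76.7% | 4.9 |
| 0.5 | 20% | 0.10 | 20.25/48.15 = 42.1% | 40.6/51.85 = 78.3% | 9.8 |
| 1 | 10% | 0.10 | 42.1% | 78.3% | 9.8 |
| 1 | 20% | 0.20 | 21.5/46.3 = 46.4% | 43.7/53.7 = 81.4% | 19.6 |

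The last column is 225 × *q* × 0.435. The sensitivities and specificities at *f* = 1 also describe the BSE-first patients alone under randomized order. With a stronger rule as baseline (75%/75%, an assumption), the same four settings give 76.2%, 77.5%, 77.5% and 80.0% for both measures.

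**The case against.** The case on the other side has force on several points.

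- **Blinding is stated repeatedly, and the record review is for medical history.** Read together, the review can be taken as subject to the blinding. That is fair as to intention. What is missing is any procedure that achieves it or checks it.
- **The leak is inferred.** The only places the documents show for bedside results and diet recommendations are the study forms, and diet is advanced only where indicated. This stands: a visible order or note is plausible, not stated.
- **Video scoring of PAS may already be intended.** The shared-recording sentence mentions scoring, and PAS is the plan's scale for scoring FEES trials. If a video PAS by a BSE-blind reader governs, most of the concern goes away. The text does not say so, and the bedside form points the other way.
- **The model is generous to the concern.** The outcome is PAS of 6 or more on any feeding, so turning an aspirator into a non-aspirator means re-scoring every positive bolus. Of the 43.5 discordant patients per 100, 31 are of that kind. The real effect may be smaller than the table shows.

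A reader might infer that the plan reserves its best-protected reading for secondary measures. The documents do not support this: onset time and bolus clearance are Aim 2 primary outcomes, and the single observer is not said to be blinded to the BSE or separate from the FEES examiner. A reader might also infer that scoring differences between sites and operators distort the reference. The plan does not give the number of FEES raters, and it foresees fidelity review of the recordings.

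**Conclusion.** The point holds as an unprotected risk to the Aim 1 reference standard. Followed as written, the plan allows the FEES examiner to learn the bedside result in BSE-first patients and then to set the primary outcome. It does not name which PAS score governs.

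It would go too far to conclude that the blinding is broken or that the results are biased by a known amount. Entry of the BSE result in the record is an inference and the pull is assumed. On the 38%/75% baseline, the assumed 10% to 20% pull adds about 2 to 4 points of sensitivity and 2 to 3 of specificity across the cohort under 1:1 order. It adds about 4 to 8 and 3 to 6 points among BSE-first patients, or in everyone if the BSE always comes first. The larger figures should not be quoted for the whole cohort under randomized order. The baseline is one pilot consistency, not the prediction rule.

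The statements on exam order differ and must be reconciled, because they decide how many patients are exposed.

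**What to change.** Two changes, each about a sentence:

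1. In 3. FEES examination, limit the FEES SLP's record review to entries made before the first study exam. Alternatively, give that SLP a history prepared by the coordinator that leaves out swallow notes and the current diet order.
2. In 3. FEES examination, Part 2, and in the paragraph on shared recordings, state that the primary-outcome PAS is the score given from the de-identified recording. The existing video observer can give it, provided that person has no access to BSE data and did not perform that patient's FEES. Keep the live score for clinical use, and report agreement between the two.

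The first change costs almost nothing. The second uses recordings, sharing and a video observer that the plan already has, but it adds work. The FEES form lists 11 boluses, so 11 × 225 = 2,475 extra readings. If the 3-ounce water test counts toward the outcome, up to 225 more are needed, 2,700 in all. If the existing observer does not meet the two conditions, another reader is needed for the affected recordings.
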